generally regarded as the most effective of these therapies and is generally used as an initial treatment for patients who first present with GERD symptoms. Nonetheless, many patients experience continued symptoms despite taking PPIs³⁰. Many patients who do not find relief with PPIs have functional heartburn symptoms and/or co-occurring dyspepsia symptoms (e.g., upper abdominal discomfort, bloating, and gas) that do not respond well to this class of medication^{31,32}. Moreover, awareness of the interconnections between the central nervous and gastrointestinal systems has led to the recognition that stress can profoundly affect gastrointestinal (GI) symptoms, such as GERD³³, suggesting that interventions targeting these pathways may improve symptoms³⁴. Notably, the placebo response rate in trials of GERD medications can be as high as 40%³⁵.

Many individuals with GERD symptoms who do not respond to PPIs have functional heartburn which is defined as less than 4% acid exposure on pH manometry and esophageal hypersensitivity^{36,37}. These patients respond better to neuromodulators such as tricyclic antidepressants, serotonin reuptake inhibitors, gabapentin, and other agents.

Amitriptyline is a tricyclic antidepressant originally used to treat depression but now frequently prescribed in low doses to treat functional GERD-related symptoms as well as functional dyspepsia, irritable bowel, fibromyalgia, and interstitial cystitis as well as other pain-related conditions^{36,38}.

[figure not shown]
Omeprazole is a PPI that is used as a first line treatment for patients who initially present with GERD symptoms.

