4. SELECTION AND ENROLLMENT OF PARTICIPANTS

4.1 Inclusion Criteria

Research subjects eligible to receive amitriptyline must meet all of the following inclusion criteria to participate in the study:

- Adults ages 24-70 years old (rationale: population of interest, GERD frequency increases with age; amitriptyline is not recommended in older adults and may have increased risk of suicidality in adults younger than 24)
- Functional heartburn (defined as <4% of time with reflux on 24 hour pH manometry) symptoms 3 or more days per week with an average daily symptom severity of 3 or more on a 7-day baseline symptom diary (see section 6.2.2 for description of instrument; rationale: subjects must be symptomatic enough that improvement in symptoms is detectable. This threshold is similar to that seen in my pilot study⁶⁴).
- English language proficiency (rationale: feasibility)
- Willingness to be videotaped and connected to physiologic monitoring devices during the visit (rationale: feasibility/study procedures)
- Willingness to take amitriptyline daily for 8 weeks following study visit 1 (rationale: feasibility/study procedures)

Research subjects eligible to receive omeprazole must meet all of the following inclusion criteria to participate in the study:

- Adults age 24 and older
- Heartburn symptoms 3 or more days per week with an average daily symptom severity of 3 or more on a 7-day baseline symptom diary
- English language proficiency
- Willingness to be videotaped and connected to physiologic monitoring devices during the visit
- Willingness to take omeprazole daily for 8 weeks following study visit 1

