9.5 Outcomes

A combination of description statistics, pearson correlations, and general linear models (GLM) such as ANCOVA, will be used for analyzing the data.

Assessment	Time Points Collected	Analysis Plan	Section
Demographics, health behaviors, height & weight	Visit 1	Descriptive statistics	9.6
Daily GERD Symptom Diary	Visit 1 & Visit 2	Primary Outcome – ANCOVA analysis adjusting for baseline GERD symptom severity and visit type using follow-up GERD symptoms as the outcome.	9.5.1
GERD-HRQL	Visit 1 & Visit 2	Descriptive statistics and secondary measures of GERD symptom severity in ANCOVA analyses.	9.6
NIH PROMIS GERD			
GSRS			
Current Stress	Visit 1 (both before & after provider visit) & Visit 2	Descriptive statistics and covariate in GLM analyses.	9.6
PSS-10	Visit 1 (before provider visit) & Visit 2	GLM to determine whether perceived stress is a modifying factor for change in GSR and HRV in the context of the visit intervention	9.6
FFI	Visit 1	GLM to determine whether personality is a modifying factor for change in GERD symptoms in the context of the visit intervention	9.6
GSR & HRV	Visit 1	Secondary Outcome – GLM assessing change in GERD symptom severity and physiologic concordance in patient-provider dyads	9.5.1
Video Recording	Visit 1	Secondary Outcomes - GLM to compare the frequency of supportive provider behaviors between the standard and expanded visit groups and responders vs. non-responders (those with a 50% or greater improvement in GERD symptoms).	9.5.2
Impressions of the Study Physician	Visit 1, post-intervention	GLM to determine whether empathy and the patient-provider connection modify change in GERD symptoms in the context of the visit intervention	9.6
CARE			
HEAL Patient-Provider Connection			

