9.5.1 Primary Outcome

1. Change in the average daily GERD symptom severity score from baseline to the last week of the study in the expanded vs. standard group. GERD symptom severity is based on the sum of scores assessing the severity of daytime heartburn, nighttime heartburn, and acid reflux each on a 0-4 point scale (none, mild, moderate, severe, very severe; higher scores signify worse symptoms). We will use ANCOVA for the primary analysis, adjusting for baseline GERD symptom severity and visit type assignment using the 8 week follow-up GERD symptom severity as the outcome. Potential moderators that will be assessed in exploratory analyses will include gender (both patient and provider), race, visit length, patient stress, personality type, and perceived connection with/empathy of the provider.

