9.5.2 Secondary Outcomes

1. To analyze physiologic synchrony in GSR, first, an average slope of the GSR will be calculated in the patient and provider recordings in moving 5 second windows, offset by 1 second. Next, Pearson correlations with lag zero will be calculated over successive 15 second windows between time-locked patient and provider GSR slope values. Then, a single session index will be calculated from the ratio of the sum of the positive correlations across the entire visit divided by the sum of the absolute value of the negative correlations across the entire visit. To reduce skew, the natural logarithm of the index will be calculated. Thus, an index value of zero reflects equal positive and negative correlations, a value greater than zero reflects more concordance in GSR than not, while a value less than zero reflects less concordance in the dyad (less than 50%)⁸². These index values will be used in GLM analyses with GERD symptom severity and/or correlated with visit type.

We will also perform similar analyses on the HRV data – comparing variation in the beat-to-beat intervals over short segments of time and calculating Pearson correlation coefficients for time-locked patient and provider data for these intervals.

2. We will calculate absolute changes in both GSR and also high frequency HRV within study subjects from the beginning to the end of the study visit. We will assess the Pearson correlation between these changes and reported changes in GERD symptom severity. We will also look at absolute levels of GSR and HRV at the end of the study visit and compare those values with changes in GERD symptom severity in GLM models. As an exploratory analysis, I will test whether changes in GSR and HRV are a function of baseline perceived stress and if that relationship differs between the standard and expanded visit interventions.
3. To analyze study visit videos, 2 minute thin slices of each video at three time points (beginning, middle, and end of study visits) will be analyzed by trained and blinded coders, for the presence of 1) micro-level non-verbal supportive behaviors (e.g., gazes, smiles, nods, gestures – measured as absolute number or

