length of time) as well as 2) macro-level impression ratings of the interaction (e.g., engagement, friendliness, relaxed, empathic, reciprocity – measured on a 1-9 scale). The PI will meet weekly with the coders to review findings and resolve areas of disagreement until greater than 70% concordance is achieved between coders using Cronbach's alpha. Each of these variables will be assessed in a GLM examining time, visit type, and time x visit type effects. We will also calculate the Pearson correlation coefficient for each variable relative to improvement in GERD symptoms and construct a GLM examining patient and provider smiling as a predictor of improvement in GERD symptoms. Other models may also be constructed based on the results of the initial video analyses.

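### The marker correlations in 9.5.2 use raw symptom improvement, which contains the baseline score, so a marker that only tracks entry severity can appear to predict improvement

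*Combined protocol and SAP*

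**What the plan says.** Section 9.1 (validity and reliability, item 2) defines change as the baseline diary average minus the average over the last 7 days, so a positive value is improvement and baseline is one of its two components.

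The marker analyses in section 9.5.2 use that quantity in two ways.

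- **Simple correlations.** For within-visit change in GSR and high-frequency HRV (item 2): "We will assess the Pearson correlation between these changes and reported changes in GERD symptom severity". For the video variables (item 3), the plan will "calculate the Pearson correlation coefficient for each variable relative to improvement in GERD symptoms".
- **General linear models with unlisted covariates.** End-of-visit GSR and HRV levels (item 2): the plan will "compare those values with changes in GERD symptom severity in GLM models". Synchrony (item 1): "These index values will be used in GLM analyses with GERD symptom severity and/or correlated with visit type"; the table in section 9.5 describes this as "GLM assessing change in GERD symptom severity and physiologic concordance in patient-provider dyads". Item 3 adds a model with patient and provider smiling as predictors of improvement.

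The primary analysis in section 9.5.1 takes another form: ANCOVA "adjusting for baseline GERD symptom severity and visit type assignment using the 8 week follow-up GERD symptom severity as the outcome". Baseline severity is named as a covariate only there. Entry requires an "average daily symptom severity of 3 or more on a 7-day baseline symptom diary" (section 4.1), and that diary also supplies the baseline.

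**The concern.** Secondary objective 1 (section 1.2) is to find physiologic markers associated with symptom improvement, and hypotheses 2, 3 and 5 in section 9.1 are statements about such associations. Subjects with a high baseline tend to show a larger baseline-minus-follow-up difference whenever follow-up rises by less than one point per point of baseline. Anything correlated with baseline then inherits part of that relation.

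Randomization balances baseline between visit types, but it does nothing for markers, which are observed and not assigned. The plan's rationale gives a possible route from entry severity to the markers: "stress can profoundly affect gastrointestinal (GI) symptoms" (section 2.1), and section 2.2 treats GSR and HRV as indicators of stress versus relaxation. At stake is whether a sign of how ill the patient was at entry gets reported as a marker of response.

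**Working it through.** **The plan's own figure.** The only power statement is the minimal detectable difference in section 9.2 (30 per group, 80% power, two-sided 0.05). A noncentral t calculation with 58 degrees of freedom gives 1.103, 1.471 and 1.839 for SDs of 1.5, 2.0 and 2.5, against the stated 1.10, 1.47 and 1.84. It reproduces. It concerns the primary comparison only; nothing comparable is given for the markers.

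**Inputs.** From the documents: n = 60, two-sided 0.05, scale 0 to 12 (three items scored 0 to 4), entry cut at 3. Assumed: r, the correlation of baseline B with follow-up F; k, the follow-up SD divided by the baseline SD; and rho, the correlation of marker M with B.

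**Formula.** Suppose M has no relation to F once B is known. Scale B to SD 1, so that F = r·k·B + error. Then

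corr(M, B − F) = rho × (1 − r·k) / √(1 + k² − 2·r·k).

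With k = 1 and no entry cut:

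- r = 0.3: 0.7/√1.4 = 0.59, so the spurious correlation is 0.18 at rho = 0.3 and 0.30 at rho = 0.5.
- r = 0.5: 0.5/√1.0 = 0.50, giving 0.15 and 0.25.
- r = 0.7: 0.3/√0.6 = 0.39, giving 0.12 and 0.19.

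At n = 60 a correlation is significant above 0.254 in absolute value.

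**How often the raw correlation is significant for such a marker (simulation):**

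| Setting | rho | r = 0.3 | r = 0.5 | r = 0.7 |
|---|---|---|---|---|
| No entry cut, k = 1 | 0.3 | 27.8% | 20.9% | 14.1% |
| | 0.5 | 64.1% | 49.8% | 31.3% |
| Cut at 3; mean 5, SD 1.8; rho set before the cut | 0.3 | 16.6% | 12.8% | 9.8% |
| | 0.5 | 39.6% | 28.4% | 18.0% |
| Cut at 3; mean 5, SD 2; rho set among enrolled subjects | 0.3 | 20.5% | 16.1% | 11.2% |
| | 0.5 | 51.3% | 36.3% | 23.3% |

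The last setting has follow-up 1.5 points lower with SD 2, clipped to 0–12. With baseline in the model, the rate in these settings is about 4% to 5%.

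**Where the bias disappears.** It is zero when r·k = 1 (r = 0.5, k = 2, rho = 0.5, no cut: 5.1%). Above that it reverses (r = 0.7, k = 2, rho = 0.5, no cut: mean correlation −0.13, significant in 17.9%). With the cut and k = 1.5, r = 0.5, rho = 0.5, the rate is only 8.1%.

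**A different null marker.** Now let the marker follow stable underlying severity, which the 7-day diary measures with error, and let it be unrelated to true change. Baseline mean 5, SD 2, cut at 3–12; follow-up 1.5 lower, SD 2, clipped; rho of 0.3 / 0.5 before the cut:

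| r | Raw-change correlation | Baseline-adjusted test |
|---|---|---|
| 0.3 | 8.0% / 14.2% | 42% / 92% |
| 0.5 | 6.6% / 10.5% | 28% / 74% |
| 0.7 | 6.6% / 8.1% | 16% / 45% |

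Here the adjusted test is the misleading one, because one noisy diary does not remove all of the underlying severity.

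**Requiring both.** The chance that both tests are significant cannot exceed the smaller of the two. It is therefore at most about 5% for a marker that follows the observed baseline, and at most about 6% to 15% for one that follows underlying severity.

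**The case against.** The strongest objection is that baseline adjustment is not plainly superior here. For a predictor that was not randomized, change score against ANCOVA is the choice behind Lord's paradox, and the return to 5% after adjustment holds only if the marker follows the observed diary score. The second simulation table bears this out, so replacing the raw correlation by the adjusted coefficient alone cannot be defended.

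Three other limits also stand.

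- A reader might infer that every marker analysis leaves baseline out. That is certain only for the Pearson correlations. Section 9.5 allows general linear models such as ANCOVA, lists current stress as a covariate, and leaves the other covariates open. The plan also calls its primary outcome a change while analysing follow-up given baseline, so the word change in a model does not prove that a raw difference is meant.
- A reader might infer that the entry threshold creates the problem. The coupling comes from baseline being part of the difference. The cut narrows the baseline range and weakens the coupling: 20.9% falls to 12.8% at rho = 0.3 and r = 0.5.
- The documents do not support any particular rho. Section 9.5.2 treats dependence of GSR and HRV changes on baseline stress as an exploratory question, and no link between entry severity and provider smiling or synchrony is stated.

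None of this supplies a baseline term for the correlations in items 2 and 3, and the GLM covariates still need to be prespecified.

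**Conclusion.** The point holds in limited form. The Pearson correlations in items 2 and 3 of section 9.5.2 can present a marker of entry severity as a marker of improvement. With the entry cut, r of 0.3 to 0.7, rho of 0.3 to 0.5 and similar spread before and after treatment, this happens in roughly 9% to 50% of trials instead of 5%. All of those correlations and SDs are assumptions.

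It would be too strong to conclude that any marker related to entry severity will appear predictive. At r = 0.5 with the cut, and rho set among enrolled subjects, such a marker is non-significant in 84% of trials at rho = 0.3 and 64% at rho = 0.5 (100 − 16.1 and 100 − 36.3, rounded). A marker negatively related to severity would appear to predict less improvement.

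For the models on end-of-visit levels, synchrony and smiling, the defect is an unstated covariate list. Responder comparisons use a 50% relative criterion and are outside this point. The primary comparison and its detectable differences are untouched. The change is worth making, but it concerns secondary, mechanistic conclusions only.

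**What to change.** In section 9.5.2, for each association between a marker and improvement, add the primary model form beside the raw-change correlation: week-8 severity as outcome, baseline severity and visit type as covariates, and the marker as predictor, with the partial correlation reported. State the same covariates for the models on end-of-visit GSR and HRV, synchrony and smiling, and align the section 9.5 table.

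Under hypotheses 2, 3 and 5, call a variable a marker of improvement only when both analyses are significant and agree in direction. A positive correlation with improvement corresponds to a negative coefficient on week-8 severity, so the plan should say how signs are compared. If the two disagree, report both and draw no marker conclusion.

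The cost is SAP wording, one degree of freedom per model for baseline (plus one for visit type), and a somewhat stricter criterion that lowers power for a true marker. Baseline severity is already collected. The joint rule does not guarantee 5% in every scenario, but it guards against the larger error of each method used alone.

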4.2 Exclusion Criteria

Any candidates eligible to receive an 8-week supply of amitriptyline meeting any of the following exclusion criteria at baseline will be excluded from study participation.

- Diagnosis of Crohn's disease, systemic sclerosis, known active ulcer disease, gastric cancer, or untreated/active Barrett's esophagitis based on subject self-report and/or medical record review (rationale: heartburn symptoms may be due to another, more serious medical illness)

- Heavy alcohol use (> 6 drinks/week for women and > 13 drinks/week for men) based on subject self-report (rationale: can exacerbate heartburn symptoms)
- Pregnant, attempting to become pregnant, or breast-feeding (rationale: feasibility/medical safety - amitriptyline is not recommended in pregnancy or breast-feeding and the physiology of heartburn is different in pregnant women).
- Dementia or significant memory difficulties as determined by the study team and medical record review (rationale: feasibility and human subjects concerns)
- Severe, unstable psychiatric disease based on subject self-report, study team determination, and/or medical record review (rationale: feasibility and human subjects concerns)
- Bipolar disorder, concurrent treatment with a SSRI or another antidepressant that interacts with tricyclic antidepressants (rationale: medical safety)
- Prolonged QTc or severe heart disease (rationale: medical safety – amitriptyline can prolong cardiac conduction).
- History of seizure disorder (rationale: medical safety – amitriptyline can lower the seizure threshold).
- Severe liver impairment – e.g., cirrhosis, hepatocellular carcinoma, hepatitis (rationale: medical safety, not recommended in patients with hepatic impairment).
- Currently taking a tricyclic antidepressant, allergy to tricyclic antidepressants, or another medical contraindication to taking amitriptyline or related medications (rationale: safety and feasibility).
- Greater than 15 doses of nonsteroidal anti-inflammatory drugs (NSAIDS) within the prior 30 days (aspirin \leq 325 mg daily permitted) or ongoing NSAID use at a level deemed likely to interfere with the study (rationale: NSAIDS can exacerbate GERD and cause peptic ulcers)
- Failure to complete the baseline symptom diary for at least 6 of 7 days (rationale: feasibility)

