5.3 Concomitant Interventions

5.3.1 Allowed Interventions

Subjects are permitted to remain on all baseline medications, over-the-counter products, and dietary supplements, including those used to treat GERD symptoms during the study. We will request that they not change doses of medications used to treat GERD symptoms during the 8 weeks that they are enrolled in the study.

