6. STUDY PROCEDURES

6.1 Schedule of Evaluations for Subjects/Patients

Assessment	Telephone Screening: (Day -30 to -7)	Baseline, Enrollment, Randomization: Visit 1 (Day 0)	Post Intervention: Visit 1 (Day 0)	Follow-up: Visit 2 (Day 53 - 60)
Screening Form	X	X		
GERD Daily Symptom Diary Reviewed		X		X
Informed Consent Form		X		
Current Medication List		X		X
Height and weight		X		
Demographics & Health Behaviors		X		
Blood Draw (optional)		X		X
GERD-Health Related Quality of Life Questionnaire (GERD-HRQL)		X		X
Patient Reported Outcomes Measurement Information System (PROMIS) GERD		X		X
Gastrointestinal Symptom Rating Scale (GSRS)		X		X
Perceived Stress Scale-10 (PSS-10)		X		X
Current Stress Question		X	X	X
NEO Five Factor Inventory (NEO-FFI)		X		
Randomization		X		
HRV, respiratory rate, skin temperature, and GSR		X		
Video recording		X		
Study visit		X		
Impressions of the Study Physician			X	
Consultation And Relational Empathy questionnaire (CARE)			X	
HEAL Patient-Provider Connection			X	
Adverse Events				X
Debriefing				X

Schedules of Evaluations for Providers

Assessment	Enrollment	Prior to each subject/patient encounter	After each subject/patient encounter	After the last study visit
Informed Consent Form	X			
Interpersonal Reactivity Index (IRI)	X			
NEO-FFI	X			
Demographics	X			
Intervention Training	X			
PSS-10		X		
Current Stress Question		X		
Fatigue Scale		X		
Physician Satisfaction Questionnaire			X	
Interview at completion of study				X

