9.2 Sample Size and Randomization

The combined standard deviation (root mean square error) in my pilot fellowship study was 1.5⁶⁴. We are conservatively assuming that this number will likely be larger in this study given the greater number of providers involved. Given 30 subjects in each group (n=60 total), 80% power, a two-sided significance test with alpha = 0.05, the minimal detectable difference (MDD) in GERD symptom severity scores between the standard and expanded groups given the estimated standard deviations (SD) is shown in the adjacent table. These MDD values are similar to those found in my fellowship study⁶⁴ and are clinically meaningful^{86,87}.

Minimal Detectable Difference Between Groups	
SD	MDD
1.5	1.10
2.0	1.47
2.5	1.84

Treatment Assignment Procedures

A randomization scheme will be devised before the start of the study by the study biostatistician who will retain the code and will be responsible for breaking the blind at the end of the study. We do not anticipate a need to break the blind during the study because we are not expecting serious adverse events to occur more frequently in one visit group than another. Randomization will be stratified by provider, with permuted block sizes of 2 and 4 with a goal to have 5-6 providers each see 10-12 subjects. If a provider cannot commit to this many visits, the study biostatistician may need to adjust the randomization scheme and we will consent additional providers.

The study biostatistician will enter the randomization scheme into REDCap and subjects will be randomized immediately prior to the study visit intervention.

If a subject drops out or is unable to complete the study, the statistician may need to rebalance the randomization scheme.

Subjects will be informed of their visit group assignment during the debriefing at the end of the second study visit.

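### The GSR/HRV-to-symptom analyses pool two non-randomised drug groups without naming study drug as a covariate, so a marker could correlate with improvement partly because it marks the drug group

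*Combined protocol and SAP*

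**What the plan says.** Section 9.5.2 contains three kinds of physiology-to-symptom analysis, each run over all subjects together.

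- Within-visit change in GSR and high-frequency HRV (item 2): "We will assess the Pearson correlation between these changes and reported changes in GERD symptom severity". No covariate is given.
- End-of-visit GSR and HRV levels (item 2): the plan will "compare those values with changes in GERD symptom severity in GLM models". The covariates are not listed.
- Concordance index (item 1): "These index values will be used in GLM analyses with GERD symptom severity and/or correlated with visit type". Again no covariates are listed. Section 9.1 also compares concordance between symptom responders and non-responders.

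The only covariate named for GLMs in general is the Current Stress item (table in Section 9.5). Study drug appears in no covariate, moderator or subgroup list in Sections 9.5 to 9.6. Use of GERD medication appears in Section 9.6 only as a descriptive variable.

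Study drug is chosen according to diagnosis and the treating physician's plan (Section 4.3, Patient Screening). Randomisation is of visit type and is stratified by provider only (Section 9.2).

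Eligibility differs by drug. The amitriptyline list in Section 4.2 excludes prolonged QTc, severe heart disease, current tricyclic use and "Bipolar disorder, concurrent treatment with a SSRI or another antidepressant that interacts with tricyclic antidepressants". The omeprazole list has none of these exclusions. Section 4.1 limits the amitriptyline group to ages 24 to 70, while the omeprazole criterion reads "Adults age 24 and older". Under Section 5.3.1, "Subjects are permitted to remain on all baseline medications".

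**The concern.** Randomising visit type protects the comparison of expanded with standard visits. It does not protect an association between a physiologic marker and later symptom change, which is observational. If the two drug groups differ on average in both the marker and the amount of improvement, pooling them produces a correlation even when none exists within either group. If the two differences have opposite signs to a true link, pooling can hide that link.

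Both differences are plausible from the protocol's own text. On the outcome side, the groups have different conditions and drugs: functional heartburn treated with a neuromodulator, and other heartburn treated with a PPI. On the marker side, people with heart disease or on antidepressants can enter one group and not the other. The protocol itself ties lower HRV to cardiovascular mortality (Section 2.2).

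Secondary objective 1 (Section 1.2) is to identify physiologic markers associated with improvement. A difference between drug groups could be reported as such a marker.

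**Working it through.** **The plan's own figure.** Section 9.2 assumes "Given 30 subjects in each group (n=60 total), 80% power, a two-sided significance test with alpha = 0.05" and gives minimal detectable differences of 1.10, 1.47 and 1.84 for SDs of 1.5, 2.0 and 2.5. A two-sample t-test (noncentral t, 58 df) has 80% power at a standardised difference of 0.7355. Multiplying by the SDs gives 0.7355 × 1.5 = 1.103, 0.7355 × 2.0 = 1.471 and 0.7355 × 2.5 = 1.839. The stated figures reproduce. They concern the randomised comparison; the plan gives no figure for the physiology correlations.

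**Inputs for this check.** From the documents: N = 60, two-sided alpha 0.05, Pearson test. Assumed, because the documents give no value: the share p on one drug (50% or 25%), and the between-drug-group differences in marker (dx) and symptom change (dy), in within-group SDs, from 0 to 1.2. For scale, at the pilot SD of 1.5, differences of 0.5, 0.8 and 1 SD in symptom score are 0.75, 1.2 and 1.5 points.

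**Induced correlation.** With zero correlation inside each drug group and q = p(1 − p), the expected pooled correlation is

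r = q·dx·dy / √[(1 + q·dx²)(1 + q·dy²)].

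At p = 0.5, q = 0.25:

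- 0.5 SD on both: 0.0625 / 1.0625 = 0.059
- 0.8 SD on both: 0.16 / 1.16 = 0.138
- 1 SD on both: 0.25 / 1.25 = 0.200

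**False-positive rate.** 40,000 simulated trials of 60 subjects per row. The unadjusted Pearson test has 58 df; the test adjusted for drug group has 57 df.

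| Drug split | dx | dy | Expected r | Unadjusted | Adjusted for drug |
|---|---|---|---|---|---|
| 50:50 | 0 | 0.8 | 0.000 | 4.9% | 5.1% |
| 50:50 | 0.3 | 0.5 | 0.036 | 5.7% | 4.8% |
| 50:50 | 0.5 | 0.5 | 0.059 | 7.2% | 5.1% |
| 50:50 | 0.5 | 0.8 | 0.090 | 10.5% | 5.1% |
| 50:50 | 0.8 | 0.8 | 0.138 | 18.2% | 5.0% |
| 50:50 | 1.0 | 1.0 | 0.200 | 34.1% | 5.1% |
| 25:75 | 0 | 0.8 | 0.000 | 5.2% | 5.0% |
| 25:75 | 0.5 | 0.5 | 0.045 | 6.3% | 4.9% |
| 25:75 | 0.8 | 0.8 | 0.107 | 12.7% | 4.8% |
| 25:75 | 1.0 | 1.0 | 0.158 | 22.6% | 5.0% |

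**How large must the differences be to do it alone?** The critical |r| at N = 60 is 0.254. For drug grouping alone to give an expected r of that size with dx = dy = d, solve q·d²/(1 + q·d²) = 0.254, so q·d² = 0.341. This gives d = 1.17 at a 50:50 split and d = 1.35 at 25:75.

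**The case against.** The strongest reply is that no passage says the two groups differ in autonomic status. The documents show only that eligibility differs, and even that is not clean. The Précis and Section 3 give 24 to 70 for the whole study, against the open-ended omeprazole criterion in Section 4.1; those passages need reconciling. This stands. The concern is that the groups may differ, not that they do.

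Second, the quoted correlation uses change within a visit, so stable differences in level between subjects cancel. Nothing documented says that within-visit change differs by drug group, and if it does not, there is no bias (rows with dx = 0). This largely stands, although absolute change can still depend on the starting level. The exposure is greater for end-of-visit levels. For the concordance index, the documents offer no reason to expect a difference by drug.

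Third, a reader might infer that the study drug itself moves the marker. It cannot. Physiology is recorded during Visit 1, and the medication is handed over when that visit ends (Sections 5.2 and 6.1).

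Fourth, a gap in improvement is not documented either. Section 2.1 says functional patients do poorly on PPIs and better on neuromodulators, but here each group receives the drug suited to it. Section 4.3 mentions recruiting patients who have not tried a PPI, yet the omeprazole criteria allow a stable PPI regimen. Different improvement is plausible, not established.

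Fifth, for the GLMs the fault is silence, not a decision to leave drug out. Section 9.6 also tests demographic factors as modifiers of improvement. That is true, but study drug is still not named, and the Pearson correlation has no place for a covariate.

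Lastly, the schedule lists "HRV, respiratory rate, skin temperature, and GSR", and a reader might conclude that high-frequency HRV must be adjusted for breathing. That is a separate and debatable choice: slower breathing may be part of the relaxation response that secondary hypothesis 3 sets out to test.

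**Conclusion.** The concern holds in a limited form. Every physiology-to-symptom analysis in Section 9.5.2, items 1 and 2, pools two drug groups that were not formed by randomisation. None names study drug. Some of an observed association could therefore reflect drug group.

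The size is unknown, because it depends on between-group differences and a drug split that the documents do not give. Differences of 0.5 SD on both variables raise the false-positive rate only from 5% to about 6–7%. The 34% figure needs 1 SD on both and a 50:50 split.

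A reader might infer that a marker would look predictive only because of drug group. That would take differences of about 1.2 SD or more on both variables, and the documents do not support it. Nor does the point reach the primary comparison. Visit type is randomised, so leaving drug out of that ANCOVA can cost precision but does not confound it.

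The change is still worth making: adjustment returned the error rate to 4.8–5.1% in every scenario, at almost no cost.

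**What to change.** In Section 9.5.2, items 1 and 2, state that every association between a physiologic measure and GERD symptom change will be estimated by a partial correlation or linear model that includes study drug. This covers within-visit change, end-of-visit level, the concordance index and the responder comparison. Report the unadjusted estimate and the estimates within each drug group alongside.

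Age may be added as a second covariate or in a sensitivity analysis; it is collected at Visit 1. Adjustment for respiratory rate is at most an optional sensitivity analysis. I would not exclude recordings on heart rhythm, since no rhythm assessment is scheduled, and I would not require a covariate for medication with autonomic effects, which the plan does not define.

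The cost is SAP wording and one degree of freedom out of 60, or two with age. No new data are needed and the sample-size figures do not change. By-drug estimates will be imprecise, especially if one drug group is small, and should be presented as descriptive.
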